### Design and Outcomes

The study design that will be piloted is a two-armed randomized embedded pragmatic clinical trial (ePCT). This pilot trial aims to determine if it is possible to use the study design to determine if cognitive decline is experienced less commonly among intervention group (defined as those receiving V-CST referral) participants than control group members based on three widely used measures of cognition, the Montreal Cognitive Assessment (MoCA), St. Louis University Memory Screen (SLUMS), and Mini Mental State Exam (MMSE).

The study population will be persons with mild cognitive impairment and/or mild to moderate dementia identified by clinicians from two memory clinics: James E. C. Walker M.D. Memory Assessment Program at the University of Connecticut (UConn), and the Yale Memory Clinic at the Yale School of Medicine (Yale).

Participants will be randomized to the intervention and control groups stratified by site at the individual level. A total of 168 eligible participants will be enrolled in the study across the two sites. Participants will be randomized at each site by a random number generator to be allocated into the intervention or control arms in a 1:2 ratio. Analysis will examine baseline demographic, diagnosis, medication, and cognitive screening variables between the two groups to ensure their balance.

Patients randomly assigned to the intervention group will be referred by their clinical providers to participate in V-CST, and those who accept the referral will participate in one of seven V-CST groups. Up to eight participants will join each group. Open enrollment into the study will close once the groups are filled with up to 56 participants or when all seven V-CST groups have begun. 112 participants will be in the control group.

The primary clinical outcome is clinically meaningful cognitive decline per scores on standardized cognitive measures (i.e., MoCA, SLUMS, MMSE) and the secondary clinical outcomes are prescribed psychotropic medications. Both are obtained during standard of care in the two sites. Outcomes to assess implementation feasibility include the referral acceptance rate, participant attendance, and attrition.

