### **Sample Size and Population**

The target population is people with mild cognitive impairment and/or mild to moderate dementia, and the study population will include those who are English-speaking and web users from one of the two health care system sites. 168 study participants will be enrolled into the study; 56 participants will be randomly assigned to the intervention group (V-CST referral) and 112 participants will be allocated to the control group to receive the current standard of care (no V-CST referral).

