### **9.2 Sample Size and Randomization**

168 people with mild cognitive impairment and/or mild to moderate dementia will be enrolled into the study, and 56 will be assigned to the intervention group through randomized allocation to receive V-CST referral, and 112 participants will be randomly allocated to the control group to receive the current standard of care (no V-CST referral). Randomization will be stratified by site by a random number sequence in a 1:2 ratio.

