## 9.5 Data Analyses

Data analysis will be conducted in two phases: after baseline data retrieval; and after all study data have been retrieved.

**After baseline data retrieval**, data analysis will be conducted to compare and assess the equivalence of baseline cognitive impairment, medications, and demographic characteristics across the intervention group and control group. Statistical analyses of baseline characteristics between participants for primary and secondary outcomes are the following: The Shapiro-Wilk test will be used to confirm that the random sample is normally distributed for the outcome variables studied. Student t-test will be used to confirm that mean variables are not significantly different between intervention and control groups (e.g., percentage with moderate versus mild cognitive impairment). Chi-square test will be used to confirm that dichotomous variables (e.g., sex) are not significantly different between intervention and control groups. Wilcoxon rank-sum will be used to confirm that ordinal variables (e.g., cognitive screening score) are not significantly different between groups.

Three outcome measures in this pragmatic study are used to assess cognition: MoCA, MMSE and SLUMS. 2-points change in the MoCA, MMSE or SLUMS will be used to indicate clinically meaningful cognitive change (either improvement or decline). Additionally, the number of points change on the cognitive screening instruments that are indicative of meaningful change will be evaluated using a distribution-based approach based on baseline cognitive assessment data from the three sites to inform the selection of instruments and threshold cut-offs for clinically meaningful change for a full-scale trial.

**After all study data have been retrieved**, including baseline and follow-up data from intervention and control groups, MoCA, SLUMS, and MMSE data elements will be examined for their completeness/missingness, and findings of missing data will be reported to the respective HCS. In addition to evaluating the completeness/missingness of data (i.e., the percentage of complete (non-missing) data elements), we also will determine the frequency of use of the three instruments (i.e., the percentage of study participants who were assessed with each instrument). If the outcomes could not be retrieved for some individuals, we will use multiple imputation with chains equations to address the missingness.

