Data analysis to test the study hypotheses is described below.

Testing of H1 will entail comparing the proportions of clinically meaningful reduction in cognitive function between the intervention group and the control group. Factors that affect the primary outcome will be controlled for by logistic regression analyses, which include the number of health comorbidities, baseline cognitive function, number of psychotropic medications, diagnoses and sites. With the study sample size, assuming that the rate of reduction in cognitive function is 50% we would be able to detect a 22% decrease in the rate of cognitive decline with 80% power and nominal level of 5%.

Testing of H2 will entail comparing the proportions of clinically meaningful improvement in cognitive function between the intervention group and the control group. Factors that affect the primary outcome will be controlled for by logistic regression analyses, which include the number of health comorbidities, baseline cognitive function, number of psychotropic medications, diagnoses and sites.

Testing of H3 and H4 will entail comparing the marginal prevalence of new prescriptions for or increased dosages of psychotropic medications between the intervention group and the control group. Logistic regression would be used to adjust for baseline clinical and demographic characteristics as in H1.

Testing of H5 will entail calculating the marginal percentage of intervention group participants who accepted the referral, the percentage that accepted the referral who enroll in V-CST, the percentage of V-CST sessions attended by enrolled participants, and the percentage of enrolled participants who ceased

attending V-CST between S1 and the last session S14. To adjust for baseline clinical and demographic variables we will use logistic regression.

Because some patients who are randomized to the intervention group may not assent to the V-CST referral, we also will conduct a secondary principal stratification analysis (Frangakis & Rubin, 2022). This analysis would be used to estimate the effect of the intervention among patients who complied with the treatment (i.e., participants assigned to the intervention group who enroll in V-CST) by performing principal stratification analysis to adjust for those participants assigned to the intervention group who did not enroll in V-CST. We will follow the analysis used in Mealli & Imbens (2004) and Hirano et al (2000).

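### The H1–H4 analyses and the H1 power figure take no account of V-CST groups in the intervention arm; the effect depends on an intraclass correlation and an uptake that the plan does not give

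*Combined protocol and SAP*

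**What the plan says.** Randomization is by person: "Participants will be randomized to the intervention and control groups stratified by site at the individual level" (Précis, Design and Outcomes). Section 9.2 adds that "Randomization will be stratified by site by a random number sequence in a 1:2 ratio", and the Précis fixes the numbers: "56 participants will be randomly assigned to the intervention group (V-CST referral) and 112 participants will be allocated to the control group".

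Treatment in the intervention arm is then shared. According to the Précis, "those who accept the referral will participate in one of seven V-CST groups", and "Up to eight participants will join each group". Section 5.1 has two facilitators running each session together. Controls receive no referral and are not grouped.

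For H1, Section 9.5 compares proportions between arms and adjusts by logistic regression for comorbidities, baseline cognition, psychotropic count, diagnoses and site. H2 to H4 are handled in the same way. The power statement is made "assuming that the rate of reduction in cognitive function is 50" per cent, and claims that "we would be able to detect a 22% decrease in the rate of cognitive decline with 80% power and nominal level of 5" per cent. No therapy-group effect, robust variance, ICC or design effect is given anywhere. The review by group in Section 9.3 concerns discontinuations for adverse events and does not enter the efficacy analysis.

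**The concern.** This is a partially nested design: one arm is clustered by therapy group and the other is not. Group members share facilitators, discussion and peers for 14 sessions, and Section 5.2 lets facilitators adapt sessions to each group. If outcomes within a group become correlated as a result, the intervention-arm proportion is less precise than 56 independent people would make it. Ordinary logistic regression does not see this, so its standard errors are too small, its intervals too narrow, and its type I error above the nominal 5%.

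The power sentence rests on the same independence assumption, so the detectable difference that it gives is on the optimistic side.

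**Working it through.** **Inputs from the documents.** 56 intervention, 112 control; 50% decline, taken as the control rate; 22% decrease; 80% power; 5% level (sidedness not stated); at most seven groups of at most eight.

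**Assumptions, because the documents give no figure.** ICC 0.01, 0.02, 0.05 or 0.10. Uptake u of 100%, 75% or 50%, spread over seven groups, so group size m is 8, 6 or 4. The unadjusted two-proportion test stands in for the adjusted model.

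**Step 1: reproduce the stated power.** Two-sided pooled test, independent participants, 28% versus 50%.
- Pooled proportion = (56 × 0.28 + 112 × 0.50)/168 = 0.4267.
- SE under the null = √[0.4267 × 0.5733 × (1/56 + 1/112)] = 0.0809.
- SE under the alternative = √[0.28 × 0.72/56 + 0.50 × 0.50/112] = 0.0764.
- Power = Φ[(0.22 − 1.96 × 0.0809)/0.0764] = Φ(0.803) = 78.9%. Without pooling it is 82.1%.
- The difference detectable with 80% power is 22.3 points.

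So the plan's figure is an absolute 22-point fall with independent, complete data. A one-sided test (87.2%), a continuity correction (73.5%) and a relative 22% decrease, 50% to 39% (26.7%), do not reproduce it.

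**Step 2: allow for groups in the intervention arm only.** Its variance is multiplied by DE = 1 + u(m − 1) × ICC; the control variance is unchanged. Example with full uptake and ICC 0.05: DE = 1 + 7 × 0.05 = 1.35.
- Type I error of the planned test: with 1:2 allocation, true SE/planned SE = √[(2 × DE + 1)/3] = √(3.70/3) = 1.111. The effective critical value is 1.96/1.111 = 1.765, a two-sided error of 7.8%.
- Power with a corrected SE: the two SEs become 0.0899 and 0.0842, so power = Φ[(0.22 − 1.96 × 0.0899)/0.0842] = Φ(0.520) = 69.9%.
- Rejection rate of the planned test for the same effect: the uncorrected 0.0809 stays in the critical value, giving Φ[(0.22 − 1.96 × 0.0809)/0.0842] = 76.7%.

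The detectable difference is found by solving the corrected-SE formula for 80% power.

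| Uptake (group size) | ICC | DE | Type I, planned test | Rejects at 22 points, planned test | Power, corrected SE | Detectable difference (points) |
|---|---|---|---|---|---|---|
| 100% (8) | 0.01 | 1.07 | 5.5% | 78.4% | 77.0% | 22.7 |
| | 0.02 | 1.14 | 6.1% | 78.0% | 75.2% | 23.2 |
| | 0.05 | 1.35 | 7.8% | 76.7% | 69.9% | 24.5 |
| | 0.10 | 1.70 | 10.6% | 74.9% | 62.0% | 26.5 |
| 75% (6) | 0.01 | 1.04 | 5.3% | 78.6% | 77.9% | 22.5 |
| | 0.02 | 1.08 | 5.6% | 78.4% | 76.9% | 22.8 |
| | 0.05 | 1.19 | 6.5% | 77.7% | 73.9% | 23.5 |
| | 0.10 | 1.38 | 8.0% | 76.5% | 69.2% | 24.7 |
| 50% (4) | 0.01 | 1.02 | 5.1% | 78.8% | 78.5% | 22.4 |
| | 0.02 | 1.03 | 5.2% | 78.7% | 78.1% | 22.5 |
| | 0.05 | 1.08 | 5.6% | 78.4% | 76.9% | 22.8 |
| | 0.10 | 1.15 | 6.2% | 77.9% | 74.9% | 23.3 |

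If the same 50% were placed in fewer groups filled to eight, DE at ICC 0.05 would be 1 + 0.5 × 7 × 0.05 = 1.175, type I error 6.4% and corrected power 74.3%.

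**Step 3: few clusters.** The corrected powers above use a normal approximation. A Satterthwaite t-test at full uptake has only about 11 to 15 degrees of freedom and gives 74.9%, 67.4% and 59.3% at ICC 0.01, 0.05 and 0.10, some 2 to 3 points lower.

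**Step 4: missing outcomes, kept separate.** If 20% were missing (an assumption), complete cases would be 44.8 and 89.6. The Step 1 formula then gives power of about 69% and a detectable difference of about 25 points, with no clustering.

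**The case against.** The best defence has four parts.

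**No ICC is known.** Delivery is by one provider under one manual, and the outcome is measured individually in clinic. If the referral changed nobody's outcome, grouping after randomization could not invalidate the comparison; inflation needs groups that truly differ around a zero average effect. This stands, and makes the size conditional. At ICC 0.01 little changes.

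**Not everyone will be grouped.** Under intention-to-treat (Section 9.5), people who decline stay in the arm ungrouped. Section 4.3 screens people at orientation and stops referrals at 56. This also stands, and is why the table runs over uptake.

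**The planned test loses little power.** A reader might infer that the H1 model fails to deliver its 80%. The documents do not support that. Over the settings in the table, the planned test rejects for a 22-point effect 74.9% to 78.8% of the time, against 78.9% under independence. Its main fault is excess type I error; most of the power loss appears only once the standard error is corrected.

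**It is a pilot.** Section 10.1 gives feasibility as the main purpose of delineating outcome measurement. A reader might infer that overstated precision will be carried into a full-scale trial, but Section 9.5 carries forward the choice of instruments and thresholds, not the effect or its standard error. This lowers the priority. It does not remove the point, because H1 is still named the primary hypothesis and has a power and a significance level attached.

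Two further inferences fail. Power near 27% follows only from reading the decrease as relative, which does not reproduce the plan's figure. Nor does the plan forecast a rate of loss: it says only that "If the outcomes could not be retrieved for some individuals, we will use multiple imputation with chains equations to address the missingness".

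**Conclusion.** The omission is real and its direction is certain for any positive group-induced ICC: the planned standard errors for H1 to H4 are too small, and the H1 power statement holds only for independent participants with complete outcomes. The size is not known. Over assumed ICCs of 0.01 to 0.10, type I error is about 5.5% to 10.6% at full uptake, 5.3% to 8.0% at 75%, and 5.1% to 6.2% at 50% uptake in groups of four. Corrected power for 22 points is about 77% to 62%, 78% to 69%, and 78.5% to 75% respectively, before any small-sample correction. These are analytic figures for an unadjusted comparison; ICC and uptake are assumptions. Dilution of the effect by people who do not enrol is a separate matter and is not counted. For a feasibility pilot this should be fixed, but it does not undermine the trial.

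**What to change.** 1. Carry the V-CST group identifier into the de-identified analysis file. CaringKind already records attendance at each session (Sections 5.1 and 5.4), but the transfer list in Section 10.2 does not name the group.
2. In Section 9.5, analyse H1 to H4 with V-CST group as the cluster for enrolled intervention participants, and each control and each non-enrolled intervention participant as a cluster of one. Use a partially nested model, or cluster-robust variance with a small-sample (Satterthwaite-type) degrees-of-freedom correction.
3. Report the ICC with its interval, and say that at most seven groups will estimate it imprecisely.
4. Restate the power sentence along these lines: *22 percentage points (50% versus 28%) assuming independent participants and complete outcomes; about 23 to 26.5 points for an assumed ICC of 0.02 to 0.10 at full uptake, less at lower uptake, before small-sample correction.* Give any allowance for missing outcomes separately and label it as an assumption.

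The cost is wording, one extra variable, somewhat wider intervals and a less favourable stated figure. No extra participants or visits are needed, and enrolment should not be increased on this account.

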## **10 DATA COLLECTION AND QUALITY ASSURANCE**

### **10.1 Data Collection Forms**

In accordance with this IMPACT Funding Opportunity (RFA-IMPACT-20-P02B), the main purpose of delineating outcome measurement is to demonstrate the feasibility of collecting the outcome measures pragmatically during the pilot study. Currently, even though the participating HCSs in Connecticut are university-based clinics using Epic, few data elements are commonly recorded in the EHRs across HCSs, limiting their research value. During this project, we will use the demographic and health data that are available in EHR and other clinical records, including data on the primary study outcome, cognitive impairment, as well as a V-CST log maintained by CaringKind as part of their standard practice.

### **10.2 Data Management**

Data from the HCSs will be gathered through a targeted raw data pull that includes only select information about study participants from the EHRs. First, clinical sites will retrieve patient data from their records based on the study inclusion/exclusion criteria, including demographic information, medications, diagnoses, and cognitive function (MoCA, SLUMS, and/or MMSE).

The research sites Yale and UConn will share data directly with UMass via Sharepoint, and will include data on V-CST enrollment, attendance, attrition, fidelity to the treatment administration manual, adverse events, and three measures standardly collected before and after participation in V-CST, the Geriatric Depression Scale, Engagement and Independence in Dementia Questionnaire - Subscales 3-5, and the Positive Psychology Outcome Measure. CaringKind will provide patient data to the referring HCS physician per standard of care. Once data is securely transferred to UMass, all study data will be stored in Microsoft Teams which is a HIPAA compliant password protected server only accessible to the UMass research team.

Confidentiality of participant records will be maintained by HCSs uploading all data to a secured server in a Sharepoint file. Access to the Sharepoint file will be limited to the PI and study coordinator at UMass, who will clean and deidentify data and assigning a unique study identifier for each participant. The UMass team will maintain a de-identified and PHI enrollment internally for communication between the research sites to ensure HIPAA compliance and protection against loss of confidentiality. UMass will be the primary location for all data management, maintenance, and distribution. All data will then be transferred from Sharepoint into MS teams to be maintained and clean accessible to only the UMass team. Sharepoint will only be used to transfer data and will not be the primary storage platform. MS teams is a HIPAA compliant and password protected platform maintained and stored on a UMass IT server. The de-

identified data will be transferred it to the study biostatistician at Brown University in an encrypted email. Using the deidentified data provided by UMass, [name], study biostatistician, will conduct data analysis, interpret results, and report findings to the PI also through encrypted email messaging.

Since the beginning of initiation of this protocol at University of Maryland, Baltimore, [name] has transition to a new appointment at University of Massachusetts. With sponsor approval, this project and protocol implementation will continue with [name] at UMass. During the regulatory and administrative transition of the project to UMass, [name] at UMB will oversee the data storage and maintenance at UMB. After a data transfer agreement is in place, [name] will securely transfer via Sharepoint. All UMB servers will be scrubbed of all data for this project and will not store any data.

### **10.3 Quality Assurance**

#### **10.3.1 Training**

Training for the CST facilitators is provided by St Louis University in affiliation with their Geriatric Workforce Enhancement Program supported by the Health Resources and Services Administration (HRSA) of the U.S. Department of Health and Human Services (HHS). All V-CST facilitators have completed this training for their scope of practice and CaringKind qualifications. Qualifications for V-CST facilitators are reviewed and approved by their employer CaringKind.

All research staff will review the study protocol and study documents prior to study initiation with the PI and study coordinator and sign a protocol training log.

#### **10.3.2 Quality Control Committee**

The PI, study coordinator, and biostatistician will serve as the study Quality Control Committee. The Quality Control Committee will review two types of reports.

1. The following reports from the V-CST facilitators will be examined:
  - V-CST Enrollment Reports, which indicate the number of intervention group members that received referral for V-CST who ultimately enrolled in V-CST
  - Adherence Reports indicating whether each participant attends each session,
  - CST protocol adherence checklists from each session, and
  - AE reports.
2. Additionally, the following report from the study coordinator will be examined:
  - Data Collection Issue Reports.

The Quality Control Committee will review the reports every two weeks during the enrollment, therapy delivery, and data collection phases of the trial, and in the unlikely case of AEs will review the AE reports within 5 business days of the reported AE. All AE that are serious or unexpected, and unanticipated problems will be reported immediately upon the facilitators or referring physicians being notified of the event. Based on the committee's review of the reports, opportunities to improve the quality of the trial design will be identified. Pending the committee's determination, official trial protocol adjustments will be made, or follow-up questions will be addressed as appropriate to the expert consultants from one or more of the IMPACT Collaboratory cores, from the HCSs, or from primary stakeholders (people with dementia) through the IMPACT Collaboratory Stakeholder Engagement Team.

